The most common clinically significant chemistry abnormalities were liver-related abnormalities, and the most common abnormality was ALT increased. The majority of treatment-emergent liver abnormalities were Grade 1 or 2; however, 13 subjects (5.7%) experienced a treatment-emergent Grade 3 or 4 ALT laboratory abnormality, and all of these subjects had previously used androgens. All but 1 subject with a Grade 3 or 4 ALT stopped androgens 7 to 9 days from first dose of BCX7353; 1 subject stopped androgens < 2 months from the first dose of BCX7353. No subject had synthetic dysfunction or evidence of hepatitis. Subjects were mostly asymptomatic, although a few subjects had abdominal symptoms that overlapped with the GI symptoms reported with BCX7353 treatment; no subject had signs or symptoms of acute hepatitis. The Grade 3 or 4 ALT elevations in the 13 subjects were primarily laboratory abnormalities without clinical symptoms. All 13 subjects improved or recovered, 5 subjects while continuing on BCX7353; 2 subjects subsequently discontinued study drug for unrelated reasons (perceived lack of efficacy in both subjects). A total of 15 subjects had postbaseline ALT > 3 × upper limit of normal (ULN; 2 subjects with nontreatment emergent ALT values). Of the subjects who had stopped androgens within the previous 2 weeks before initiating BCX7353, the incidence of subjects with ALT > 3 × ULN was 32.5%. Of the subjects with ≥ 5 years of androgen use, the incidence of subjects with ALT > 3 × ULN was 13.0%. One subject had a bilirubin > 1.5 × ULN although no subject had a Grade 3 or Grade 4 bilirubin, and no subject had a concurrent elevation in bilirubin > 1.5 × ULN and ALT or AST > 3 × ULN. No subject met the criteria for Hy's law during the study.

In summary, BCX7353 was safe and generally well tolerated with no new safety signals observed.

Subjects treated with BCX7353 110 or 150 mg QD had durably low attack rates, with no evidence for the development of tolerance to BCX7353. After 1 month of treatment, the 73 subjects in the BCX7353 150 mg dose group who received BCX7353 through Week 48 had a mean (SD) attack rate of 1.18 (1.40) attacks per month. The mean rate of attacks held relatively steady during Months 2 to 12: 1.01 (1.26) attacks per month in Month 6 and 0.81 (1.03) attack per month in Month 12.

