8.3.2. Subject Discontinuation from Study Drug

A subject will be permanently withdrawn from study drug for any of the following bulleted reasons, which will be recorded in the source documents and CRF. When medically feasible, the Medical Monitor must be consulted prior to subject discontinuation. In all cases, subjects who prematurely and permanently discontinue study drug should complete all scheduled procedures for the end-of-study visit outlined in Table 3.

- Emergence of any laboratory abnormality or AE that in the judgment of the Investigator compromises the ability of the subject to continue study-specific procedures or it is considered not to be in the subject's best interest due to an altered benefit-risk profile
- Reoccurrence of treatment-emergent AST or ALT elevation $> 5 \times \text{ULN}$ (confirmed) if BCX7353 is restarted after meeting hold criteria as outlined in Section 12.2.2.
- Treatment-emergent ALT or AST $> 3 \times \text{ULN}$ combined with either laboratory abnormalities indicative of significant hepatic toxicity (ie, meeting Hy's law, total bilirubin $> 2 \times \text{ULN}$ OR with an INR > 1.5) or with symptomatology of acute hepatitis (ie, severe fatigue, nausea, vomiting, right upper quadrant pain and tenderness, fever, rash, and/or eosinophilia [$> 5\%$])
- Subsequent determination that inclusion/exclusion criteria were not met
- Intercurrent illness or emergence of a new illness/medical condition that would, in the judgment of the Investigator, affect assessments of clinical status to a significant degree
- Subject noncompliance with study drug or to the protocol
- Subjects with BCX7353-related Grade 3 or 4 rash as described by the Division of Microbiology and Infectious Diseases (DMID) criteria "skin-mucocutaneous" will be discontinued from study, if suspected to be due to BCX7353, and treated according to best medical practice. All subjects with a suspected drug rash should undergo specific rash evaluation as described in Section 11.1.12. A Grade 3 rash is defined as vesiculation or moist desquamation or ulceration, and a Grade 4 rash is defined as exfoliative dermatitis, mucous membrane involvement or erythema multiforme or

suspected SJS or necrosis requiring surgery. Subjects with a Grade 1 or 2 study drug-related rash may continue BCX7353 if the Investigator and subject deem it appropriate.

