12.1.8. Treatment Interruptions

Treatment interruptions as a result of Investigator management of AEs potentially related to study drug are permissible. Resumption of study drug administration is also permissible upon resolution of the event, as assessed by the Investigator, with a plan for stringent monitoring of the subject for recurrence of the AE as appropriate. In addition, other extenuating circumstances may lead to treatment interruptions such as vomiting during an abdominal HAE attack or required fasting for medical procedures; in these cases, study drug should be resumed once the extenuating circumstance is resolved.

The Sponsor Medical Monitor should be notified in the event of a treatment interruption due to an AE. Any treatment interruption will be recorded in the CRF and source documents, including the reason for the interruption.

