12.2.2. Aminotransferase (ALT or AST) Elevation

All baseline or treatment-emergent ALT or AST elevations $> 3 \times \text{ULN}$ (ie, Grade 3 and above) should be confirmed within 72 hours with repeat assessment of ALT and AST as well as total bilirubin, ALP, prothrombin time /INR, and complete blood count for eosinophil levels. If subjects are asymptomatic with no other pertinent laboratory abnormality, study drug may be continued under close observation with every 2 week assessment of transaminase levels, total bilirubin, and ALP. These may be done at a local laboratory as long as results are reported to the Investigator as soon as they are available and the investigative site contacts the subject to ascertain any symptoms. If either ALT or AST continue to increase and the subject remains asymptomatic, study drug dosing must be held if:

- Either ALT or AST is $> 5 \times \text{ULN}$ for more than 2 weeks
- The ALT or AST reaches $> 8 \times \text{ULN}$

The subject should continue regular assessments as deemed appropriate by the Investigator of ALT, AST, total bilirubin, ALP, prothrombin time/INR, and complete blood count for eosinophil levels until ALT and/or AST are $< 3 \times \text{ULN}$.

Provided specific criteria are met, the Investigator and subject may elect to resume BCX7353 dosing. All of the following criteria must be met for dosing to resume:

- The subject is considered to have been deriving benefit from BCX7353 prior to holding study drug.
- Transaminases return to $\leq 2 \times \text{ULN}$ for subjects whose baseline transaminase levels were above the ULN, and $\leq \text{ULN}$ for those whose baseline transaminase levels were $\leq \text{ULN}$.
- Subjects have not initiated or restarted androgens during the period BCX7353 was held.
- The subject agrees to continue every 2 week monitoring of ALT, AST, total bilirubin, ALP, CBC (eosinophil levels) and prothrombin/INR until levels appear stable and

transaminase levels remain $< 3 \times \text{ULN}$ for at least 1 month after restarting BCX7353 dosing.

If at any time, the criteria as outlined in Section 8.3.2 is met, the study drug must be permanently discontinued.

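### The mandatory ALT/AST hold in protocol Section 12.2.2 requires a rising value, so a flat, asymptomatic value already above 5 × ULN for more than 2 weeks has no mandatory hold

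*Protocol*

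**What the plan says.** Protocol Section 12.2.2 requires a repeat within 72 hours for any ALT or AST above 3 × ULN. If the subject has no symptoms and no other relevant laboratory finding, "study drug may be continued under close observation with every 2 week assessment of transaminase levels", along with total bilirubin and ALP. That sentence sets no upper limit and no time limit.

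The mandatory part follows: "If either ALT or AST continue to increase and the subject remains asymptomatic, study drug dosing must be held if" one of two conditions is met. The first is ALT or AST above 5 × ULN for more than 2 weeks. The second begins "The ALT or AST reaches" and gives a level above 8 × ULN.

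Section 8.3.2 has two numeric liver rules for permanent withdrawal:

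- A confirmed recurrence above 5 × ULN, "if BCX7353 is restarted after meeting hold criteria as outlined in Section 12.2.2".
- ALT or AST above 3 × ULN "combined with either laboratory abnormalities indicative of significant hepatic toxicity" (total bilirubin above 2 × ULN, or INR above 1.5) or with symptoms of acute hepatitis.

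The remaining provisions rest on judgment. Section 8.3.2 also lists "Emergence of any laboratory abnormality or AE that in the judgment of the Investigator compromises" continued participation or the subject's interest. Section 12.1.8 adds: "Treatment interruptions as a result of Investigator management of AEs potentially related to study drug are permissible". Section 14.4 says that no formal stopping rules exist beyond those in Section 8.3.

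**The concern.** A limit on how long a value may stay above 5 × ULN is a test of persistence, but the lead-in also demands a rise. Taken together, the rule leaves out the steady elevation that a persistence test would be expected to catch. A site that follows the text exactly may keep dosing because the value is not climbing.

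Two features of the plan make a flat first value plausible. After Week 24 the scheduled visits are 24 weeks apart (Section 10.3.4), so an elevation may be at or past its peak when first seen. The exclusion criteria in Section 8.2.2 set no numeric ALT or AST limit, and Section 12.2.2 covers elevations present at baseline as well as those that emerge on treatment.

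Section 5.7 names transaminase elevation as one of two important potential risks. A mandatory rule on that risk should not depend on how a site reads its opening clause. There is also a secondary effect: if the Investigator holds drug by judgment, the Section 12.2.2 criteria may not have been met, and the recurrence rule in Section 8.3.2 may then not apply after restart.

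**Working it through.** **The rule as a logical condition.** Section 12.2.2, read literally:

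HOLD = rising AND asymptomatic AND (above 5 × ULN for more than 2 weeks OR above 8 × ULN).

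**Test case.** An asymptomatic subject has a first, confirmed ALT of 6 × ULN that stays at 6 × ULN for 4 weeks, with normal bilirubin and INR and no earlier hold.

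| Provision | Condition needed | Met? |
|---|---|---|
| 12.2.2 mandatory hold | Rising value | No |
| 8.3.2 recurrence | Earlier hold under 12.2.2, then restart | No |
| 8.3.2 combined rule | Bilirubin, INR or hepatitis symptoms | No |
| 8.3.2 judgment | Investigator's assessment | Discretionary |
| 12.1.8 interruption | Investigator's management of an AE | Permitted, not required |

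With the rising condition removed, the 5 × ULN limb is true and the hold is mandatory. The lead-in alone therefore creates the gap.

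**Two neighbouring cases.** A subject who goes from 3–5 × ULN to above 5 × ULN and then levels off can fairly be read as having continued to rise, and so as covered. For the 8 × ULN limb, the verb may itself describe arrival at that level; a first value above 8 × ULN that is flat on repeat is not clearly in or out.

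**Size of the wider group.** The documents give no count of flat values above 5 × ULN. The nearest figure is treatment-emergent Grade 3 or 4 ALT, and Grade 3 starts at 3 × ULN in the DMID table (Appendix 16.1).

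Inputs:
- Section 5.2.2: 13 of 227 subjects had Grade 3 or 4 ALT. Of these, 12 stopped androgens 7 to 9 days from first dose and 1 stopped less than 2 months from it. Androgen groups were 40 (stopped within 2 weeks), 113 (stopped earlier) and 74 (never used); 40 + 113 + 74 = 227.
- Section 8.1: about 250 US subjects.

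Exact (Clopper-Pearson) 95% intervals:

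| Scenario | Rate | 95% CI | × 250 | 95% CI |
|---|---|---|---|---|
| Washout has no effect | 13/227 = 5.73% | 3.08–9.59% | 14.3 | 7.7–24.0 |
| Rate outside the 2-week group | 1/(113 + 74) = 1/187 = 0.53% | 0.01–2.94% | 1.3 | 0.0–7.4 |

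Improved or recovered while continuing drug: 5/13 = 38.5% (13.9–68.4%).

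Assumptions: the 12 subjects at 7 to 9 days belong to the group of 40, and the remaining case does not; ALT only; both doses pooled; exposure as at the interim cut (mean 282.7 days), so counts over 96 weeks could be higher. Both rows are ceilings for ALT under their scenario, because the gap needs a level above 5 × ULN, more than 2 weeks, no rise, no symptoms and otherwise normal tests.

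**The case against.** The strongest reply is that the opening clause means escalation beyond the 3 × ULN entry level, with the two thresholds saying how far or how long. On that reading most plateaus above 5 × ULN are held. This stands for subjects who climbed from a lower elevation. It does not help when the first or confirmed value is already above 5 × ULN and then stays flat.

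Sparing non-rising values could also be deliberate. The sponsor had seen that "All 13 subjects improved or recovered, 5 subjects while continuing on BCX7353", and Section 5.4.3 describes the elevations as transient. The documents do not show which was intended. If a rise is meant to be required, the protocol should say so and say what happens to a plateau.

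The safeguards are real. Continuation is optional, needs a clean picture otherwise and carries 2-weekly tests; bilirubin, INR or hepatitis symptoms force withdrawal whatever the trend; and the Investigator may interrupt or stop. The recurrence problem needs a long chain (plateau, discretionary hold, restart, confirmed recurrence, and an Investigator who still does not withdraw), and nothing in the documents shows it occurring.

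A reader might infer that every asymptomatic plateau above 5 × ULN escapes the rule, that values above 8 × ULN carry no mandatory hold, or that about 14 US subjects would be exposed to the gap. The documents support none of these. The first ignores the covered climb from 3–5 × ULN, the second treats ambiguity as absence, and the third counts all Grade 3 or 4 ALT.

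**Conclusion.** The gap is real but narrow. Read literally, Section 12.2.2 requires no hold for an isolated, asymptomatic ALT or AST that is already above 5 × ULN when first seen or confirmed and stays there for more than 2 weeks without rising. No other section supplies a mandatory hold for that case. The 8 × ULN limb needs clarification.

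The number affected is unknown. It is an unknown part of a wider group projected at about 1 (0–7) to 14 (8–24) Grade 3 or 4 ALT cases per 250, under the assumptions above. The lower end is more plausible: 12 of the 13 interim cases stopped androgens at an interval that the 28-day washout (Section 5.4.3) now excludes. The affected number is probably very small and could be zero.

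This is a minor safety-rule correction, worth making because it is cheap and concerns a named risk. It does not alter any endpoint or analysis.

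**What to change.** Replace the lead-in and both bullets in Section 12.2.2 with:

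*In an asymptomatic subject, study drug dosing must be held if either ALT or AST remains > 5 × ULN for more than 2 weeks and is rising or stable (not clearly declining), or if either reaches > 8 × ULN at any time, including on the first value.*

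Add that such a hold counts as meeting the hold criteria for the recurrence rule in Section 8.3.2. The sponsor should state what counts as clearly declining.

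Two limits are deliberate. Clearly falling values are left out of the 5 × ULN limb, because 5 of the 13 interim cases improved or recovered on drug. The 8 × ULN limb should not require confirmation, since the repeat may take up to 72 hours and could delay a hold.

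Costs: a few more temporary holds. Each leaves a gap in prophylaxis until the restart limits are met (at or below ULN, or at or below 2 × ULN if baseline was raised). Restart then brings 2-weekly ALT, AST, bilirubin, ALP, CBC and prothrombin time/INR until values are stable, with transaminases below 3 × ULN for at least 1 month. The change also needs a minor amendment with IRB/IEC approval (Section 14.1.2).

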12.2.3. Overdose

To date there is no experience with overdose of oral BCX7353. Single doses of up to 1000 mg, 7 days of dosing up to 500 mg/day, and 14 days of dosing with 350 mg/day revealed no clinically significant safety concerns in healthy subjects in Study BCX7353-101. In Study BCX7353-102, multiple dosing with 350 mg BCX7353 for up to 9 days either following or current with single doses of CYP probe substrate drugs in healthy subjects overall did not reveal any new safety concerns. Safety data generated in Study BCX7353-203, 28-day dosing with up to 350 mg/day, revealed no clinically significant safety concerns in subjects with HAE. Subsequently, subjects enrolled in BCX7353-106 were exposed to BCX7353 450 mg QD for 14 days without any unexpected AEs or increased AE severity.

In the event that study personnel become aware of an overdose of study drug/IMP (≥ 150 mg per calendar day) that is associated with an AE, both the overdose and the resultant event should be reported as AEs. Overdose without any symptoms (i.e., AEs) does not need to be reported as an AE. If overdose occurs with or without associated AEs, subjects should undergo clinical and laboratory monitoring as appropriate for their clinical condition and, if indicated, should receive clinically-indicated supportive therapy.

Additional information about overdose as an AE or SAE is discussed in Section [12.1.1.2](#).

12.3. Data Monitoring Committee

Data from ongoing studies BCX7353-302 (Phase 3 study), BCX7353-301 (Phase 3 study) and the current study, BCX7353-204, are reviewed by the BCX7353 data monitoring committee (DMC). Since a total of over 200 subjects have completed 48 weeks across the studies, the DMC will be provided with data for review every 6 months until the last subject completes the study or the product is approved in the first country globally. A formal meeting of the DMC members will not be required; however, if the data review identifies any concern, the DMC members may elect to hold a formal DMC meeting. Where possible, scheduled DMC meetings for this protocol may be aligned with those of other protocol(s). The DMC may also be convened if a new clinically significant safety signal emerges or at other times as requested.

The latest data review was conducted on 23 October 2019.

The recommendation of the DMC was that all 3 studies proceed per protocol.

A separate DMC Charter will describe membership, roles, timing of DMC review, and responsibilities of the DMC members.

13. STATISTICS

13.1. Sample Size Considerations

No sample size calculations were conducted for this open-label, long-term safety study. Approximately 475 subjects may be enrolled in this study, with approximately 250 subjects planned to be enrolled in the US, to provide access to BCX7353 for additional subjects who, in the opinion of the Investigator, are expected to benefit from treatment with an oral treatment for the prevention of angioedema attacks.

13.2. Stratification

Not applicable.

13.3. Statistical Methods

A detailed SAP will be developed to describe the methods of analyses and summaries, including all endpoints, time points, populations, missing data, etc. Deviations from the analyses outlined in the SAP will be described in the CSR.

13.3.1. Analysis Populations

The analysis populations are defined below.

13.3.1.1. Screen Failures

Subjects who give written informed consent but are not assigned to study treatment and are noted as screen failures in the CRF are considered screen failures.

13.3.1.2. Safety Population

The safety population will include all subjects who received at least 1 capsule of study drug. This population will be used for all analyses of accountability, demographics, BCX7353 drug concentrations, and safety.

13.3.1.3. Intent-to-Treat Population

The intent-to-treat (ITT) population will include all subjects who are allocated to study drug. The ITT population will be used as the primary population for effectiveness analyses. Subjects will be analyzed based on the treatment to which they were allocated.

13.3.2. General Considerations for Data Analysis

In general, descriptive summaries will include n, mean, standard deviation, median, minimum, and maximum for continuous variables and n and percent for categorical variables. Summaries will be presented by treatment group and by study visit.

All individual subject data will be listed as measured. All statistical summaries and analyses will be performed using SAS[®] software (SAS Institute, Cary, North Carolina, USA).

13.3.3. Missing Data

For subjects who prematurely discontinue the study, all available data will be included for the key safety and effectiveness analyses.

13.3.4. Subject Demographic and Disposition Data

Demographic data and baseline characteristics including age, gender, race or ethnicity, height, weight, BMI, and HAE history will be summarized by treatment group.

Subject disposition will be presented for all subjects. The number of subjects who completed through each study visit and those that discontinued from the study will be provided. The reasons for early discontinuation also will be presented. A tabulation of the number of subjects exposed to study drug and duration of exposure will also be presented. Treatment adherence, dose interruptions and reason for dose interruptions will be provided as summaries or listed as appropriate.

13.3.5. Analysis of Safety Variables

Safety endpoints that will be summarized, at a minimum by treatment group, include the proportion of subjects 1) with TEAEs; 2) who discontinue BCX7353 due to TEAEs; 3) with treatment-emergent SAEs; 4) with treatment-emergent Grade 3 or 4 AEs; 5) with treatment-emergent treatment-related AEs consistent with a drug rash as identified by the Investigator (eg, maculopapular rash, papular rash identified as an EOSI), and 6) with treatment-emergent Grade 3 or 4 laboratory abnormalities.

Time to discontinuation due to a TEAE, and time to development of drug-related rash will be estimated using the Kaplan-Meier method. For those with a drug-related rash, clinical and laboratory findings will be summarized and the proportion of subjects who successfully continued therapy following onset of rash.

AEs will be mapped to a Medical Dictionary for Regulatory Activities (MedDRA) PT and SOC. The occurrence of TEAEs will be summarized using MedDRA PT, SOC, and severity. Separate summaries of TEAEs, treatment-emergent SAEs, AEs considered to be related to study drug, and AEs leading to study drug interruption will be generated. All AEs will be listed for individual subjects showing both verbatim and preferred terms.

Descriptive summaries for vital signs, weight, bedside ECG parameters, and clinical laboratory results will be presented. Laboratory abnormalities will be graded according to the DMID Adult Toxicity Table (Publish Date: Draft, November 2007; Appendix 16.1).

Any graded abnormality that occurs following the initiation of study drug and represents at least 1-grade increase from the baseline assessment is defined as treatment-emergent. The number and percentage of subjects experiencing treatment-emergent graded toxicities will be summarized. Laboratory toxicity shifts from baseline to worst postbaseline assessments will be summarized.

The number and percentage of subjects having elevations in liver enzyme abnormalities (ALT, AST, or bilirubin) in relation to fold above ULN will be summarized according to the FDA's Premarketing Clinical Evaluation on Drug-Induced Liver Injury Guidance for Industry (FDA 2009).

Clinically significant abnormal morphological ECG findings will be summarized.

The change from baseline in QTcF will be determined by routine ECGs. At each time point ECGs are analyzed, an individual subject's change from baseline will be calculated as:

$$\Delta_{ik} = (\text{QTcF for subject at time point } k - \text{Baseline QTcF})$$

Where QTcF measurements will be the average of triplicate ECGs at baseline and single values at each time point.

For routine ECGs, the number and proportion of subjects with QTcF ≤ 450 , > 450 to ≤ 480 , > 480 to ≤ 500 , and > 500 msec; or changes of ≤ 30 , > 30 to ≤ 60 , or > 60 msec will be summarized.

Physical examination findings will be listed.

Concomitant medications and those discontinued during the study will be coded using the World Health Organization drug dictionary and summarized. Subjects with medications changes prior to baseline may also be summarized.

